- Obtain blood sample for IL-6 and E-selectin measurement. This will occur monthly while patients are on study.
- Tumor assessments will be performed every 8 weeks (+/- 1 week) from randomization until the start of another anticancer therapy. A partial or complete response warrants confirmation no sooner than 4 weeks and no later than 6 weeks after its initial observation. This confirmatory scan is considered outside of standard of care, and will be funded by the sponsor.

Post-Study Assessments

- Any research participant who is discontinued from study treatment for any reason other than PD will continue to have tumor assessments every 8 weeks (+/- 1 week) until the patient starts another anticancer therapy. The investigator or his/her designee will continue collecting information on the initiation of anticancer therapies until the date of data cutoff for the final analysis. All new anticancer therapy therapies after the last dose of treatment will be recorded on the appropriate CRF.
- All research participants will be followed for survival every 6 months.

Clinical Laboratory Assessments

All clinical laboratory assessments will be performed at City of Hope. Laboratory tests should be performed at baseline, at specified visits during the study, and at the follow-up visit, all as indicated in the Time and Events Table(s). Laboratory assessments may be performed within 3 days before the actual visit to allow flexibility in scheduling. Assessments may be performed more frequently if clinically indicated.

All laboratory tests with values that become clinically abnormal while the subject is participating in the study or within 28 days after the last dose of study drug should be repeated at the PI's discretion until the values return to normal or baseline.

Results for all unscheduled clinical laboratory assessments (i.e., hematology, TSH/T₄, coagulation parameters) should be recorded on an unscheduled laboratory form in the eCRF.

Hematology and Clinical Chemistry

Appendix A shows the hematology and clinical chemistry laboratory parameters that should be reported. Assays for hematology and clinical chemistry should be performed at baseline, every 4 weeks until 6 months, and then every 8 weeks thereafter. Hepatic assays should be performed at

baseline, 2, 4, and 8 weeks, followed by every 4 weeks until 6 months, and then every 8 weeks thereafter.

Liver Function Tests

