- 3.1.11 Patients with childbearing potential, including any female who has had a negative serum pregnancy test within 2 weeks prior to the first dose of study treatment, preferably as close to the first dose as possible, and agrees to use adequate contraception. GSK acceptable contraceptive methods, when used consistently and in accordance with both the product label and the instructions of the physician, are as follows: (1) complete

abstinence from sexual intercourse for 14 days before exposure to investigational product, through the dosing period, and for at least 21 days after the last dose of investigational product, (2) oral contraceptive, either combined or progestogen alone, (3) injectable progestogen, implants of levonorgestrel, estrogenic vaginal ring, percutaneous contraceptive patches, intrauterine device (IUD) or intrauterine system (IUS) with a documented failure rate of less than 1% per year, (4) male partner sterilization (vasectomy with documentation of azoospermia) prior to the female subject's entry into the study, and this male is the sole partner for that subject, (6) double barrier method: condom and an occlusive cap (diaphragm or cervical/vault caps) with a vaginal spermicidal agent (foam/gel/film/cream/suppository) Female subjects who are lactating should discontinue nursing prior to the first dose of study drug and should refrain from nursing throughout the treatment period and for 14 days following the last dose of study drug.

3.1.12 Adequate organ system function as defined in Table 1

Table 1. Definitions for Adequate Organ Function

System	Laboratory Values
Absolute neutrophil count (ANC)	$\geq 1.5 \times 10^9/L$
Hemoglobin	$\geq 9 \text{ g/dL (5.6 mmol/L)}$
Platelets	$\geq 100 \times 10^9/L$
Prothrombin time (PT) or international normalized ratio (INR) ^a	$\leq 1.2 \times \text{ULN}$
Activated partial thromboplastin time (aPTT)	$\leq 1.2 \times \text{ULN}$
Total bilirubin	$\leq 1.5 \times \text{ULN}$
Alanine amino transferase (ALT) and Aspartate aminotransferase (AST) ^b	$\leq 2.5 \times \text{ULN}$
Serum creatinine	$\leq 2.0 \text{ mg/dL (133 } \mu\text{mol/L)}$
Or, if $>2.0 \text{ mg/dL}$: Calculated creatinine clearance (ClCR) by Cockroft-Gault formula	$\geq 30 \text{ mL/min}$
Urine Protein to Creatinine Ratio (UPC; appropriate appendix) ^c	<1

- a. Subjects receiving anticoagulant therapy are eligible if their INR is stable and within the recommended range for the desired level of anticoagulation.

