4.1.2 Assessments within 7 days of the first dose

- 4.1.2.1 Physical examinations: height (only recorded at baseline) and body weight and current medical conditions.
- 4.1.2.2 Vital signs: body temperature, blood pressure and heart rate.

Note: If a subject presents with poorly controlled hypertension, defined as SBP \geq 140mmHg or DBP \geq 90mmHg, antihypertensive medication(s) should be initiated or adjusted with a goal to control the blood pressure to $<140/90$ mmHg.

- 4.1.2.3 ECOG PS
- 4.1.2.4 Clinical laboratory assessments.
- 4.1.2.5 12-lead ECG with QTc measurement
- 4.1.2.6 Baseline IL-6 and E-selectin assessment
- 4.1.2.7 Serum pregnancy test for women of childbearing potential.

4.1.3 Pre-dose Assessments on Day 1

- 4.1.3.1 Physical examination: to identify any changes in the subject's mental and medical conditions since baseline assessment that would make him/her ineligible for the study.
- 4.1.3.2 Blood pressure measurements: subjects must have a blood pressure reading of <140/90mmHg to be eligible.
- 4.1.3.3 ECOG PS: Any changes since baseline assessment should be recorded in the eCRF. Subjects having deterioration of ECOG PS to ≥ 2 will be excluded from the study
- 4.1.3.4 Review results of all the other baseline assessments to determine the subject's eligibility for the study. Any screening laboratory results outside the normal range will be repeated (prior to the first dose) at the discretion of the Investigator. All laboratory results must be within the values outlined in the Inclusion Criteria before the first dose of study drug.
- 4.1.3.5 Record all the medication(s) received within 2 weeks prior to the first dose of study medication and indicate if the medication is continuing.
- 4.1.3.6 Obtain archived tumor tissue samples for biomarker assessments (if available).
- 4.1.3.7 Obtain a blood sample for biomarker research. It is preferable to collect the sample on the first day of dosing but the sample may be collected at any time after first dose of investigational product. **Note:** a signed written informed consent for participating biomarker research must be obtained before collecting the blood sample for biomarker analysis.

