6.1.2 Criteria for Starting Subsequent Cycles

A cycle may be repeated every 28 days (+/- 3 days) if the patient has at least stable disease and continue to meet laboratory parameters as defined in the eligibility section.

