17.0 Appendix I: Urine Protein Creatinine Ratio (UPC)

Clinical meaning of UPC

There is a good correlation between the ratio of protein concentration to creatinine concentration in a random urine sample and the amount of protein excreted over 24 hours. Creatinine excretion is fairly constant throughout the day regardless of changes in urine flow rate.

Men excrete 20 mg to 25 mg of creatinine/kg of body weight/day.

Women excrete 15 mg to 20 mg of creatinine/kg of body weight/day.

Normal protein excretion is <100 mg to 150 mg/24 hours and is similar for men and women.

Calculating UPC

UPC ratio = Urine protein (mg/dL) / Urine creatinine (mg/dL).

UPC ratio \approx equivalent to grams of protein excreted in urine over 24 hrs.

Example: Patient has a urine protein = 90 mg/dL and urine creatinine = 30 mg/dL.

UPC ratio = $(90 \text{ mg/dL}) / (30 \text{ mg/dL}) = 3$

The calculated UPC ratio is 3, which correlates to roughly 3 g protein excretion in a 24-hour period.

Units for UPC ratio

Note: To calculate UPC, protein and creatinine concentrations must be expressed in the same units (mg/dL, g/L, or $\mu\text{mol/L}$). If, for example, protein concentration is expressed in mg/dL and creatinine concentration is expressed in $\mu\text{mol/L}$, conversion of one of the concentration values is required. Conversion factors are:

From	To	Conversion Factor
Conventional Units: mg/dL	SI Units: $\mu\text{mol/L}$	Multiply by 88.4
SI Units: $\mu\text{mol/L}$	Conventional Units: mg/dL	Divide 88.4

References:

NKF: NKF KDOQI Guidelines [Internet]. National Kidney Foundation; nd. KDOQI Clinical Practice Guidelines for Chronic Kidney Disease: Evaluation, Classification, and Stratification. Available from http://www.kidney.org/professionals/KDOQI/guidelines_ckd/p5_lab_g5.htm

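### The serum creatinine limit is printed as 2.0 mg/dL (133 µmol/L); by the protocol's own factor these are two different limits, so eligibility is ambiguous between about 1.5 and 2.0 mg/dL

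*Combined protocol and SAP*

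**What the plan says.** In the protocol, Table 1 of section 3.1.12 (adequate organ function) sets the upper limit for serum creatinine at "2.0 \text{ mg/dL (133 } \mu\text{mol/L". Section 3.1.7 defers to this table for what counts as normal laboratory values.

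The next row offers another way to qualify, a minimum of 30 mL/min for "Calculated creatinine clearance (ClCR) by Cockroft-Gault formula". It applies only when creatinine is above 2.0 mg/dL, and that trigger has no SI value.

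Two other sections make the table binding:

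- Section 4.1.3.4 (pre-dose, day 1): "All laboratory results must be within the values outlined in the Inclusion Criteria before the first dose of study drug".
- Section 6.1.2: a further 28-day cycle may start if, among other things, the patient "continue to meet laboratory parameters as defined in the eligibility section".

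The unit conversion is in Appendix I (section 17.0). It says that when protein and creatinine are reported in different units, "conversion of one of the concentration values is required", and for mg/dL to µmol/L the instruction is "Multiply by 88.4". Appendix II gives Cockcroft-Gault formulas for serum creatinine in both mg/dL and µmol/L.

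**The concern.** A limit printed in two units should be one limit. Here the SI figure looks too low for the mg/dL figure beside it, by far more than rounding. If so, the table contains two thresholds, and a patient whose creatinine lies between them is eligible on one and ineligible on the other.

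The threshold decides whether a patient is enrolled, and section 6.1.2 reuses it for continuing treatment. Section 13.2.1 adds a no-deviations rule, so someone checking records against the SI figure could class as ineligible a patient enrolled in good faith on the mg/dL figure. Section 14.1.1 bases the response rate on eligible treated patients, so a disputed eligibility call can reach the denominator of the primary endpoint. With 28 patients, one patient is 1/28 = 3.6 percentage points.

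**Working it through.** **Inputs**

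- Printed limit: 2.0 mg/dL and 133 µmol/L (section 3.1.12, Table 1).
- Factor: µmol/L = mg/dL × 88.4 (Appendix I).
- Constants in the Cockcroft-Gault formulas (Appendix II): divisor 72 for mg/dL, with 0.85 for women; SI multipliers 1.23 (men) and 1.05 (women).
- Trigger of the clearance row: above 2.0 mg/dL (section 3.1.12, Table 1).

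**Step 1. Try to reproduce the printed SI figure.**

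- 2.0 × 88.4 = 176.8 µmol/L, not 133.
- 133 / 88.4 = 1.50 mg/dL, not 2.0.
- Factor that the printed pair would need: 133 / 2.0 = 66.5.

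The printed figure is not reproduced.

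**Step 2. Check that the factor applies to serum creatinine.** Appendix I gives 88.4 in the context of urine. The serum formulas in Appendix II imply their own factor:

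- Men: 1.23 × 72 = 88.56.
- Women: 1.05 × 72 / 0.85 = 88.94.

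Both agree with 88.4 to rounding. Using 88.56 or 88.94 instead puts 2.0 mg/dL at 177.1 or 177.9 µmol/L. No factor in the protocol gives 133.

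**Step 3. Size of the gap.**

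| Measure | Calculation | Result |
|---|---|---|
| Absolute, SI | 176.8 − 133 | 43.8 µmol/L |
| Absolute, conventional | 43.8 / 88.4 | 0.50 mg/dL |
| Relative to the higher limit | 43.8 / 176.8 | 24.8% |
| Relative to the lower limit | 43.8 / 133 | 32.9% |

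**Step 4. Follow one patient in the band through the table.** Take creatinine of 1.8 mg/dL, which is 1.8 × 88.4 = 159.1 µmol/L.

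- Against 2.0 mg/dL: meets the limit.
- Against 133 µmol/L: fails the limit.
- Clearance row: not open, because 1.8 is not above 2.0 mg/dL.

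On the mg/dL reading the patient is eligible. On the SI reading the patient is ineligible, and the table prints no other route.

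**Step 5. Why the clearance trigger must be considered together with the limit.** If the route were open in the band, it would not give one answer for everyone. Two illustrative patients at 1.8 mg/dL (ages and weights assumed here):

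- Man, 60 years, 80 kg: (140 − 60) × 80 / (72 × 1.8) = 49.4 mL/min, above 30.
- Woman, 75 years, 50 kg: 0.85 × (140 − 75) × 50 / (72 × 1.8) = 21.3 mL/min, below 30.

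Correcting only the limit could therefore leave the band unresolved.

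**The case against.** The strongest reply concerns consequence, since the arithmetic is not in doubt. This is a single-institution study, and the synopsis says "All clinical laboratory assessments will be performed at City of Hope"; section 6.2 likewise refers to a local laboratory. One laboratory would normally report in one unit. The mg/dL figure appears twice, in the limit and in the clearance trigger, and those two rows join without a gap. The SI figure appears once, in brackets. Staff working in mg/dL would meet no contradiction when applying the table. No part of the two-stage design depends on this cell.

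Much of this stands, and it limits two stronger readings.

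- A reader might infer that patients in the band will in practice be handled differently according to unit. The documents do not show this. They do not state the reporting unit, and nothing in them indicates that two units would be used side by side.
- A reader might infer that a patient who fails the SI figure falls back on creatinine clearance. As printed, that patient cannot, because the clearance row opens only above 2.0 mg/dL.

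The reply does not remove the discrepancy. Reporting only in mg/dL is a full defence only if 2.0 mg/dL was the intended limit. If 133 µmol/L was intended, the figure that staff would use is the wrong one. It is true that 133 is close to 1.5 mg/dL (1.5 × 88.4 = 132.6), but that does not show which number was meant.

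**Conclusion.** The point holds as an internal contradiction in a binding threshold. Under the protocol's own factor the two printed limits are 176.8 and 133 µmol/L, or 2.0 and 1.50 mg/dL. The gap is 43.8 µmol/L: about a quarter of the higher limit or a third of the lower. The limit is ambiguous for every patient between about 1.5 and 2.0 mg/dL, both at enrolment and at each later cycle start.

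The conclusion assumes only that 88.4 applies to serum creatinine, which the Appendix II constants support. The number of decisions affected cannot be estimated, because the reporting unit and the share of patients in the band are not given. If results are reported only in mg/dL and 2.0 was intended, the effect could be nil.

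Type I error, power and sample size are unaffected. The only link to the primary analysis is through who counts as eligible.

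**What to change.** Reconcile the two creatinine figures in Table 1 of section 3.1.12 so that both express one limit under the 88.4 factor. Then make the trigger of the clearance row match that limit, preferably stated in both units. Confirm that sections 4.1.3.4 and 6.1.2 are meant to use the reconciled limit. Which limit was intended is for the clinical team to decide; the documents do not settle it.

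Cost: if the SI figure changes, one table cell. If the mg/dL figure changes, two cells, because the clearance trigger repeats it. No recalculation of the design is needed. If patients have already been enrolled, a check of their baseline and cycle-start creatinine values would show whether any fell in the band.

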3.2 Exclusion Criteria

- 3.2.1 Concurrent use of other investigational agents
- 3.2.2 Known history of allergic reactions to pazopanib or other VEGF-TKIs
- 3.2.3 Presence of serious or uncontrolled infection
- 3.2.4 Prior malignancy. (Note: Subjects who have had another malignancy and have been disease-free for 3 years, or subjects with a history of completely resected non-melanomatous skin carcinoma or successfully treated in situ carcinoma are eligible.)
- 3.2.5 History or clinical evidence of central nervous system (CNS) metastases or leptomeningeal carcinomatosis, except for individuals who have previously-treated CNS metastases, are asymptomatic, and have had no requirement for steroids or anti-seizure medication for 6 months prior to first dose of study drug. Screening with CNS imaging studies (computed tomography [CT] or magnetic resonance imaging [MRI]) is required only if clinically indicated or if the subject has a history of CNS metastases.
- 3.2.6 Clinically significant gastrointestinal abnormalities that may increase the risk for gastrointestinal bleeding including, but not limited to (1) active peptic ulcer disease, (2) known intraluminal metastatic lesion/s with risk of bleeding, (3) inflammatory bowel disease (e.g. ulcerative colitis, Crohn's disease), (4) other gastrointestinal conditions with increased risk of perforation, or (5) history of abdominal fistula, gastrointestinal perforation, or intra-abdominal abscess within 28 days prior to beginning study treatment.
- 3.2.7 Clinically significant gastrointestinal abnormalities that may affect absorption of investigational product including, but not limited to (1) malabsorption syndrome or (2) major resection of the stomach or small bowel.
- 3.2.8 Corrected QT interval (QTc) > 480 msec using Bazett's formula
- 3.2.9 History of any one or more of the following cardiovascular conditions within the past 6 months: (1) cardiac angioplasty or stenting, (2) myocardial infarction, (3) unstable angina, (4) coronary artery bypass graft surgery, (5) symptomatic peripheral vascular disease, or (6) Class III or IV congestive heart failure, as defined by the New York Heart Association (NYHA)
- 3.2.10 Poorly controlled hypertension [defined as systolic blood pressure (SBP) of ≥ 140 mmHg or diastolic blood pressure (DBP) of ≥ 90 mmHg]. (Note: Initiation or adjustment of antihypertensive medication(s) is permitted prior to study entry. BP must be re-assessed on two occasions that are separated by a minimum of 1 hour; on each of these occasions, the mean (of 3 readings) SBP / DBP values from each BP assessment must be $< 140/90$ mmHg in order for a subject to be eligible for the study.)
- 3.2.11 History of cerebrovascular accident including transient ischemic attack (TIA), pulmonary embolism or untreated deep venous thrombosis (DVT) within the past 6 months. (Note:

Subjects with recent DVT who have been treated with therapeutic anti-coagulating agents for at least 6 weeks are eligible)

- 3.2.12 Prior major surgery or trauma within 28 days prior to first dose of study drug and/or presence of any non-healing wound, fracture, or ulcer (procedures such as catheter placement not considered to be major).
- 3.2.13 Evidence of active bleeding or bleeding diathesis.
- 3.2.14 Known endobronchial lesions and/or lesions infiltrating major pulmonary vessels
- 3.2.15 Hemoptysis in excess of 2.5 mL (or one half teaspoon) within 8 weeks prior to the first dose of study drug.
- 3.2.16 Any serious and/or unstable pre-existing medical, psychiatric, or other condition that could interfere with subject's safety, provision of informed consent, or compliance to study procedures.
- 3.2.17 Unable or unwilling to discontinue use of prohibited medications list as specified in the full protocol for at least 14 days of a drug prior to the first dose of study drug and for the duration of the study.
- 3.2.18 Treatment with any of the following anti-cancer therapies: (1) radiation therapy, surgery or tumor embolization within 14 days prior to the first dose of pazopanib OR (2) chemotherapy, immunotherapy, biologic therapy, investigational therapy or hormonal therapy within 14 days or five half-lives of a drug (whichever is longer) prior to the first dose of pazopanib
- 3.2.19 Any ongoing toxicity from prior anti-cancer therapy that is >Grade 1 and/or that is progressing in severity, except alopecia.
- 3.2.20 Non-Compliance: Patients, who in the opinion of the investigator, may not be able to comply with the safety monitoring requirements of the study.
- 3.2.21 Medications that inhibit CYP3A4 may result in increased plasma pazopanib concentrations; therefore, co-administration of strong CYP3A4 inhibitors is PROHIBITED beginning 14 days prior to the first dose of study drug until discontinuation from the study. Strong CYP3A4 inhibitors include (but are not limited to): certain antibiotics (including clarithromycin, telithromycin, and troleandomycin), certain HIV protease inhibitors (including ritonavir, indinavir, saquinavir, nelfinavir, amprenavir, and lopinavir), certain ntifungals (including itraconazole, ketoconazole, voriconazole, and fluconazole) and certain antidepressants (including nefazodone).

3.3 Inclusion of Women and Minorities

The study is open to all participants regardless of gender or ethnicity. Efforts will be made to extend the accrual to a representative population, but in this trial which will accrue approximately 28 patients, a balance must be struck between patient safety considerations and limitations on the number of individuals exposed to potentially toxic or ineffective treatments on the one hand and the need to explore gender, racial, and ethnic aspects of clinical research on the other. If differences in outcome that correlate to gender, racial, or ethnic identity are noted, accrual may be expanded or additional studies may be performed to investigate those differences more fully.

4.0 Screening and Registration Procedures

4.1 Screening Procedures

Diagnostic or laboratory studies performed exclusively to determine eligibility for this trial will be done only after obtaining written informed consent. Documentation of the informed consent for screening will be maintained in the patient's research chart and medical record. Studies or procedures that were performed for clinical indications (not exclusively to determine study eligibility) and within the screening window, may be used for baseline values even if the studies were done before informed consent was obtained.

4.1.1 Assessments within 28 days of the first dose

- 4.1.1.1 Medical history:
- 4.1.1.2 Renal cell carcinoma specific history including: date of diagnosis, primary tumor type with histology/cytology determination, current stage of cancer, prior systemic treatment(s) for RCC, ongoing toxicity related to prior treatment(s); and history of other malignancies
- 4.1.1.3 Prior surgery and/or radiotherapy (date, organ/anatomic region(s) of surgery and/or radiotherapy must be documented), other significant medical and surgical histories within the past 6 months.
- 4.1.1.4 Baseline bone scan for tumor assessment
- 4.1.1.5 Baseline disease assessments of chest, abdomen and pelvis using CT or MRI
- 4.1.1.6 MRI or CT of the brain within 2 weeks of first dose if clinically indicated or if the subject has a history of CNS metastases

